6.5 POOLING OF CENTRES

This section is not applicable, because the study was performed in only one centre.

6.6 HANDLING OF MISSING DATA AND OUTLIERS

Handling of missing data and outliers will be performed as described in the CTP, Section 7.5.

The only exception where imputation might be necessary for safety evaluation is AE dates. Missing or incomplete AE dates are imputed according to BI standards (see 001-MCG-156_RD-01 ([4](#))).

Missing data and outliers of PK data are handled according to BI standards (see 001-MCS-36-472_RD-01) ([5](#)).

6.7 BASELINE, TIME WINDOWS AND CALCULATED VISITS

For vital signs baseline for Period 1 is defined as the last measurement prior to first drug administration, and baseline for Period 2 is defined as the last measurement prior to first drug administration in Period 2.

For laboratory parameters baseline for Period 1 and Period 2 is defined as the last measurement prior to first drug administration, as the REP of BI 1323495 is not known.

Section 6.1 of the CTP: *Exact times of measurements outside the permitted time windows will be documented. The acceptable time windows for screening, for measurements and assessments scheduled to occur 'before' trial medication administration on Day 1, and the end of trial examination are provided in the Flow Chart.*

The acceptable deviation from the scheduled time for vital signs, ECG and laboratory tests will be ± 15 min for the first 4 h after trial drug administration and ± 30 min thereafter. Starting from 48 h post administration a deviation from the scheduled time for vital signs, ECG and laboratory tests of ± 120 min is acceptable.

If scheduled in the Flow Chart at the same time as a meal, blood sampling, vital signs, and 12-lead ECG recordings have to be done first. Furthermore, if several measurements including venepuncture are scheduled for the same time, venepuncture should be the last of the measurements due to its inconvenience to the subject and possible influence on physiological parameters.

Adherence to time windows will be checked via the consistency check listings at the RPM/DBLM.

7. PLANNED ANALYSIS

Safety analysis (refer to [Section 7.8](#)) will be performed by and will be presented in Sections 15.1 to 15.4 of the CTR and in Appendix 16.2 and 16.1.13.1.

Inferential statistical analyses of PK endpoints (refer to [Section 7.4](#) and [Section 7.5.2](#)) will also be performed by and will be presented in Section 15.5 of the CTR and in Appendix 16.1.13.3.

Descriptive data analysis of PK parameters and concentrations will be performed by the department Translational Medicine and Clin. Pharmacology at BI and will be presented in Section 15.6 of the CTR.

The format of the listings and tables will follow the standards defined in the BI corporate guideline “Reporting of Clinical Trials and Project Summaries” [001-MCG-159] ([6](#)) with the exception of those generated for PK-calculations ([7](#)).

The individual values of all subjects will be listed, sorted by treatment sequence, subject number, visit and actual treatment (if appropriate).

The listings will be included in Appendix 16.2 of the CTR.

For end-of-text tables, the set of summary statistics for non-PK parameters is:

N	number non-missing observations
Mean	arithmetic mean
SD	standard deviation
Min	minimum
Median	median
Max	maximum

For analyte concentrations as well as for all PK parameters, the following descriptive statistics will additionally be calculated:

CV	arithmetic coefficient of variation
gMean	geometric mean
gCV	geometric coefficient of variation
P10	10th percentile
Q1	1st quartile
Q3	3rd quartile
P90	90th percentile

The data format for descriptive statistics of concentrations will be identical with the data format of the respective concentrations. The descriptive statistics of PK parameters will be calculated using the individual values with the number of decimal places as provided by the evaluation program. Then the individual values as well as the descriptive statistics will be reported with three significant digits in the CTR.

Tabulations of frequencies for categorical data will include all possible categories and will display the number of observations in a category, as well as the percentage (%) for each treatment sequence/group. Percentages will be rounded to one decimal place and will be based on all subjects in the respective subject set whether they have non-missing values or not. The category 'missing' will be displayed only if there are actually missing values.

Units of variables should be given in the titles or column/row descriptors in square brackets (e.g. [mg]).

Exclusion of PK parameters

The ADS ADPP (PK parameters) contains column variables indicating inclusion/exclusion (APEXC) of a PK parameter and an analysis flag comment (APEXCO). All analyses based on the PKS will include parameters if they are not flagged for exclusion, that is APEXCO is equal to "Included".

Exclusion of PK concentrations

The ADS ADPC (PK concentrations per time-point or per time-interval) contains column variables ACEXC and ACEXCO indicating inclusion/exclusion (ACEXC) of a concentration and an analysis flag comment (ACEXCO). Exclusion of a concentration depends on the analysis flag comment ACEXCO. For example, if ACEXCO is set to 'ALL CALC', the value will be excluded for all types of analyses based on concentrations. If ACEXCO is set to 'DESC STATS' the value will be excluded from descriptive evaluations per planned time point/time interval. If ACEXCO contains the addition 'TIME VIOLATION' or 'TIME DEVIATION' the value can be used for further analyses based on actual times. If ACEXCO is set to 'HALF LIFE', the value will be excluded from half-life calculation (and, as a consequence, any calculation that relies on λz) only; the value is included for all other analyses.

Further details are given in 001-MCS-36-472_RD-01 "Noncompartmental Pharmacokinetic / Pharmacodynamic Analyses of Clinical Studies" ([5](#)) and 001-MCS-36-472_RD-03 "Description of Analytical Transfer Files and PK/PD Data Files" ([11](#)).

7.1 DEMOGRAPHIC AND OTHER BASELINE CHARACTERISTICS

Only descriptive statistics are planned for this section of the report, based on the TS.

The data will be summarised by treatment sequence and in total.

7.2 CONCOMITANT DISEASES AND MEDICATION

Frequency tables are planned for this section of the report, based on the TS.

Concomitant diseases will be coded using the coding system of the Medical Dictionary for Drug Regulatory Activities (MedDRA). Medications will be coded using the World Health

Organization Drug Dictionary (WHO-DD). The coding version number will be displayed as a footnote in the respective output.

The diagnoses and medications will be listed. Subjects without any concomitant diagnoses or concomitant therapies should be marked with a “No” in the respective column.

The relevance of the concomitant therapies to the evaluation of PK will be decided no later than at the RPM/DBLM.

7.3 TREATMENT COMPLIANCE

Section 4.3 of the CTP: *Compliance will be assured by administration of all trial medication in the study centre under supervision of the investigating physician or a designee. The measured plasma concentrations of trial medication will provide additional confirmation of compliance.*

It is not intended to list the compliance separately. Any deviations from complete intake will be addressed in the RPM/DBLM (cf. TSAP [Section 6.2](#)) and described in the CTR.

7.4 PRIMARY ENDPOINTS

Relative bioavailability of BI 1323495 is to be determined on the basis of the primary and secondary pharmacokinetic endpoints (see [Section 5.1](#)).

Section 7.3.1 of the CTP:

Primary analysis

The statistical model used for the analysis of primary and secondary endpoints will be an analysis of variance (ANOVA) model on the logarithmic scale. That is, the PK endpoints will be log-transformed (natural logarithm) prior to fitting the ANOVA model. This model will include effects accounting for the following sources of variation: sequence, subjects within sequences, period and treatment. The effect ‘subjects within sequences’ will be considered as random, whereas the other effects will be considered as fixed. The model is described by the following equation:

$$y_{ijkm} = \mu + \zeta_i + s_{im} + \pi_j + \tau_k + e_{ijkm}, \text{ where}$$

y_{ijkm} = logarithm of response measured on subject m in sequence i receiving treatment k in period j,

μ = the overall mean,

ζ_i = the ith sequence effect, i = 1, 2

s_{im} = the effect associated with the mth subject in the ith sequence, m = 1, 2, ..., 6

π_j = the j^{th} period effect, $j = 1, 2$

τ_k = the k^{th} treatment effect, $k = 1, 2$

e_{ijkm} = the random error associated with the m^{th} subject in sequence i who received treatment k in period j .

The implementation for this analysis will be accomplished by using the XPKISTAT macro, based on PKS, and option BWC (Bioavailability/Bioequivalence, within-subject design, time-controlled).

Section 7.3.1 of the CTP: *For each endpoint, the difference between the expected means for $\log(T)-\log(R)$, will be estimated by the difference in the corresponding adjusted means (Least Squares Means). Additionally, their two-sided 90% confidence intervals will be calculated based on the residual error from the ANOVA and quantiles from the t-distribution. These quantities will then be back-transformed to the original scale to provide the point estimate and 90% CIs for each endpoint.*

Further exploratory analyses

As a sensitivity analysis, this ANOVA will be repeated for the primary and secondary endpoints with all sources of variation ('sequence', 'subjects within sequences', 'period', 'treatment') considered as fixed effects. This analysis will be done using PROC GLM.

The following SAS code can be used to fit the model:

```
PROC GLM DATA=indata;
  CLASS subject treatment sequence period;
  MODEL logkp = treatment sequence period subject(sequence);
  LSMEANS treatment / PDIFF=CONTROL("Ref_trt") CL ALPHA=0.1;
  RUN;
```

7.5 SECONDARY ENDPOINTS

7.5.1 Key secondary endpoints

This section is not applicable as no key secondary endpoint has been specified in the protocol.

7.5.2 Secondary endpoints

The secondary PK parameter $AUC_{0-\infty}$ will be assessed using the same methods as described for the primary endpoints.

7.7 EXTENT OF EXPOSURE

Descriptive statistics are planned for this section of the report based on the TS. The date and time of drug administration will be listed for each subject.

7.8 SAFETY ANALYSIS

All safety analyses will be performed on the TS.

The safety data for treated subjects who failed to complete the study (dropouts or withdrawals) will be reported as far as their data are available. All withdrawals will be documented and the reason for withdrawal recorded.

7.8.1 Adverse events

AEs will be coded with the most recent version of MedDRA.

The analyses of AEs will be descriptive in nature and will be based on BI standards as presented in the corporate guideline: “Analysis and Presentation of Adverse Event Data from Clinical Trials” [001-MCG-156] ([8](#)).

The standard AE analyses will be based on the number of subjects with AEs (and not on the number of AEs).

For analysis, multiple AE occurrence data on the case report form (CRF) will be collapsed into one AE provided that all of the following applies:

- All AE attributes are identical (lower level term (LLT), intensity, action taken, therapy required, seriousness, reason for seriousness, relationship, outcome, AE of special interest)
- The occurrences were time-overlapping or time-adjacent (time-adjacency of two occurrences is given if the second occurrence started within one hour after end of the first occurrence).

For further details on summarization of AE data, please refer to [001-MCG-156] ([8.4](#)).

Section 5.1.5.1.4 of the CTP: *The following are considered as AESIs:*

- ***Hepatic injury***
A hepatic injury is defined by the following alterations of hepatic laboratory parameters:
 - *an elevation of AST (aspartate transaminase) and/or ALT (alanine transaminase) ≥ 3 -fold ULN combined with an elevation of total bilirubin ≥ 2 -fold ULN measured in the same blood sample, or*
 - *aminotransferase (ALT, and/or AST) elevations ≥ 10 fold ULN*

These lab findings constitute a hepatic injury alert and the patients showing these lab abnormalities need to be followed up according to the 'DILI checklist' provided in the ISF. In case of clinical symptoms of hepatic injury (icterus, unexplained encephalopathy, unexplained coagulopathy, right upper quadrant abdominal pain, etc.) without lab results (ALT, AST, total bilirubin) available, the Investigator should make sure these parameters are analysed, if necessary in an unscheduled blood test. Should the results meet the criteria of hepatic injury alert, the procedures described in the DILI checklist should be followed.

The analysis of adverse events will be based on the concept of treatment emergent adverse events.

Section 1.2.5 of the CTP: *The residual effect period (REP) of BI 1323495, i.e. the time interval when measurable drug levels or PD effects are still likely to be present, is not yet known. Therefore, all AEs with an onset between start of treatment and the end of trial examination (last per protocol contact) will be considered on treatment.*

All adverse events occurring before first drug administration will be assigned to 'screening', those between intake of trial medication and prior to next drug administration or termination date will be assigned to the corresponding treatment ('on treatment').

Section 7.3.4 of the CTP: AEs occurring after the last per protocol contact but entered before database lock will be reported to Pharmacovigilance only and will not be captured in the trial database.

For more detail see the TSAP ADS plan.

According to ICH E3 (9), AEs classified as 'other significant' need to be reported and will include those non-serious and non-significant adverse events with

- (i) 'action taken with trial drug = discontinuation' or 'action taken with trial drug = reduced', or
- (ii) marked haematological and other lab abnormalities or lead to significant concomitant therapy as identified by the Clinical Monitor/Investigator at the Report Planning Meeting.

An overall summary of AEs (including AESIs) will be presented.

The frequency of subjects with AEs will be summarised by treatment, primary system organ class (SOC) and preferred term (PT). Separate tables will be provided for subjects with other significant AEs according to ICH E3 (9), for subjects with serious AEs, for subjects with drug-related AEs, for subjects with drug related serious adverse events and for subjects with AESIs.

The SOC and PTs will be sorted by frequency (within SOC). The MedDRA version number will be displayed as a footnote in the respective output.

In addition, frequencies of subjects with non-serious AEs that had an incidence of > 5% for at least one treatment will be summarised by treatment, primary SOC and PT.

For disclosure of adverse events on EudraCT, additional information not included in a standard AE analysis will be performed. The following three entries will be created:

- Adverse Events per arm for disclosure on EudraCT
- Non-serious Adverse Events for disclosure on EudraCT
- Serious Adverse Events for disclosure on EudraCT

Two types of AE displays will be provided in the report:

A) Section 15.3 and Appendix 16.1.13.1.8 (for ClinicalTrials.gov and EudraCT only) of the CTR displays:

In these displays, the on treatment phase will be analysed (labelled with the name of the study treatment (short label)). Screening and follow-up periods will not be included in this analysis. The following total will be provided in addition (Section 15.3 only):

- a total over all on treatment phases included in this analysis ("Total on treatment")

B) Section 15.4 and Appendix 16.1.13.1.8 (except for ClinicalTrials.gov and EudraCT) of the CTR displays:

- Screening
- On treatment (labelled with the name of the study treatment (short label))

In Section 16.1.13.1.8 AE tables, the following totals will be provided in addition:

- a total over all study phases ("Total")

7.8.2 Laboratory data

Descriptive statistics will be calculated by treatment including change from baseline. Due to an unknown REP, baseline of period 1 will be used as baseline of both periods. The timepoints V3 -2:00 and post-exam and their change from baseline will be determined for the treatment in Period 2.

Laboratory data will be analysed qualitatively via comparison of laboratory data to their reference ranges. Values outside the reference range as well as values defined as possible clinically significant will be flagged in the data listings.

It is the investigator's responsibility to decide whether a lab value is clinically significantly abnormal or not(at the RPM/DBLM at the latest).

The analyses of laboratory data will be based on BI standards [001-MCG-157] ([10](#)).

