6.2.2 Treatment periods

Each subject is expected to participate in 2 treatment periods (Days -1, 1, 2, 3, 4 and 5 in each period). In addition, an ambulatory visit will be necessary within 3 days prior to the first study drug administration for safety laboratory. At least 6 days will separate drug administrations in the first and second treatment periods.

In the evening of Day -1 of each treatment period, study participants will be admitted to the trial site and kept under close medical surveillance for at least 24 h following drug

Proprietary confidential information © 2018 Boehringer Ingelheim International GmbH or one or more of its affiliated companies

administration. The subjects will then be allowed to leave the trial site after formal assessment and confirmation of their fitness. All following trial assessments will be performed in an ambulatory fashion.

For details on time points and procedures for collection of plasma samples for PK analysis, refer to [Flow Chart](#) and Section [5.2.2](#).

The safety measurements performed during the treatment period are specified in Section [5.1](#) of this protocol and in the [Flow Chart](#). For details on times of all other trial procedures, refer to the [Flow Chart](#). AEs and concomitant therapy will be assessed continuously from screening until the end of trial examination.

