7.3.4 Safety analyses

Safety will be analysed based on the assessments described in Section [2.2.2.2](#). All treated subjects (TS, refer to Section [7.3](#)) will be included in the safety analysis. Safety analyses will be descriptive in nature and based on BI standards. No hypothesis testing is planned.

For all analyses, the treatment actually administered (= treatment at onset) to the subject will be used (any deviations from the randomised treatment will be discussed in the minutes of the Report Planning Meeting).

Treatments will be compared in a descriptive way. Tabulations of frequencies/proportions will be used to evaluate categorical (qualitative) data, and tabulations of descriptive statistics will be used to analyse continuous (quantitative) data.

Measurements (such as ECG, vital signs, or laboratory parameters) or AEs will be assigned to treatments (see Section [4.1](#)) based on the actual treatment at the planned time of the measurement or on the recorded time of AE onset (concept of treatment emergent AEs). Therefore, measurements planned or AEs recorded prior to first intake of trial medication will be assigned to the screening period, those between first trial medication intake and end of trial termination date will be assigned to the treatment period. These assignments including the corresponding time intervals will be defined in detail in the TSAP. Note that AEs occurring after the last per protocol contact but entered before final database lock will be reported to Pharmacovigilance only and will not be captured in the trial database.

Additionally, further treatment intervals (analysing treatments) may be defined in the TSAP in order to provide summary statistics for time intervals, such as combined treatments, on-treatment totals, or periods without treatment effects (such as screening and follow-up intervals).

Adverse events will be coded using the Medical Dictionary for Regulatory Activities (MedDRA). Frequency, severity, and causal relationship of AEs will be tabulated by treatment, system organ class, and preferred term. SAEs, AESIs (see Section [5.2.5.1](#)), and other significant AEs (according to ICH E3) will be listed separately.

Previous and concomitant therapies will be presented per treatment group without consideration of time intervals and treatment periods.

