6. GENERAL ANALYSIS DEFINITIONS

6.1 TREATMENTS

For basic study information on investigational products, assignment of treatment sequences, and selection of doses, please see CTP, Sections 3 and 4.

The study will be performed as a randomised, open-label, two-way crossover trial with two treatments (T and R) and two treatment sequences (T-R or R-T).

In total, it was planned to assign 12 healthy male subjects to the two treatment sequences in a 1:1 ratio.

For details of dosage and formulation see Table 6.1: 1 below:

Table 6.1: 1 Treatments and labels used in the analysis

Treatment		Short label	Short label for footnote
T fed	tablets of BI 1323495,	BI fed	BI 1323495 fed
R fasted	tablets of BI 1323495,	BI fasted	BI 1323495 fasted

The following separate study phases will be defined for the analyses of AEs:

- **Screening** (ranging from 0:00 h on day of informed consent until first administration time of study drug)
- **On treatment** (separately for each treatment, ranging from the time of administration of the respective treatment until next drug administration of 0:00 h or on the day after trial termination date)

Please note that all AEs reported between start of trial drug administration and the last per-protocol contact will be considered on treatment (i.e. no follow-up period is considered in this trial).

Displays of AEs will be presented separately for the treatments described in [Table 6.1: 1](#) above.

For detailed information on the handling of the treatments in the O*C views refer to Technical TSAP ADS plan and Data Reviewers guide.

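### SAP 7.8.2 reports the pre-dose laboratory value of Period 2 (V3 -2:00) under a treatment the subject has not yet taken, against Protocol 7.3.4

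*SAP*

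**What the plan says.** SAP 7.8.2 plans descriptive statistics for laboratory data by treatment, including change from baseline. On the baseline it says "Due to an unknown REP, baseline of period 1 will be used as baseline of both periods". It continues: "The timepoints V3 -2:00 and post-exam and their change from baseline will be determined for the treatment in Period 2".

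Protocol 7.3.4 names laboratory parameters among the measurements to be assigned to treatments. The assignment is to be "based on the actual treatment at the planned time of the measurement or on the recorded time of AE onset". The same section leaves the detailed definition of assignments and time intervals to the SAP. SAP Section 4 states that nothing was changed relative to the protocol.

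Two other parts of the SAP deal with the same moment for other data:

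- **Vital signs (SAP 6.7):** "baseline for Period 2 is defined as the last measurement prior to first drug administration in Period 2".
- **Adverse events (SAP 7.8.1):** after the screening phase, "those between intake of trial medication and prior to next drug administration or termination date will be assigned to the corresponding treatment". SAP 6.1 defines matching phases but limits them to AEs: "The following separate study phases will be defined for the analyses of AEs".

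**The concern.** A blood sample taken before the second dose can only reflect the first treatment, or no treatment effect at all. Putting its change from the Period 1 baseline in the column of the second treatment attributes it to a condition the subject has not yet experienced. In this two-sequence crossover, that means fed-state results are shown as fasted and fasted-state results as fed.

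The SAP's own reasoning makes this harder to accept. It does not use the last value before the Period 2 dose as a laboratory baseline because the REP is unknown, so that value might still carry an effect of the first dose. The next sentence then reports the value under the other treatment.

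What is at stake is the by-treatment laboratory summary at this one time point. A change that persisted to, or first appeared at, V3 -2:00 would be summarised under the wrong food condition.

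**Working it through.** The documents give no figure to reproduce. The check compares the assignment rules and then counts where the values fall.

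**Step 1: what V3 -2:00 is.** Protocol 5.1.3 lists Visit 1 as screening, Visits 2 and 3 as a separate group with their own laboratory time points, and Visit 4 as the end-of-trial examination. Visit 3 is therefore the Period 2 treatment visit. A negative time is read as hours before dosing, so the sample is taken 2 h before the second dose.

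**Step 2: which treatment each rule gives for that moment.**

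| Rule | Applies to | Handling at V3 -2:00 |
|---|---|---|
| Protocol 7.3.4 | Measurements, including laboratory | Actual treatment at the planned time: Period 1 is the only one taken |
| SAP 7.8.2 | Laboratory | Period 2 treatment |
| SAP 6.1 and 7.8.1 | AEs only | Period 1 treatment, which runs until the next dose |
| SAP 6.7 | Vital signs | The last value before the Period 2 dose is the Period 2 baseline, so it is not a change under Period 2 |

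Only SAP 7.8.2 reports a change at this moment under the treatment still to come. An AE with onset at V3 -2:00 and a laboratory value drawn then would appear under different treatments.

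**Step 3: how many values are affected.** SAP 6.1 plans 12 subjects, randomised 1:1, so 12 / 2 = 6 per sequence. Assuming all complete and provide the sample:

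| Sequence | n | Taken by V3 -2:00 | Column under SAP 7.8.2 | Column under Protocol 7.3.4 |
|---|---|---|---|---|
| R-T | 6 | Fasted only | Fed | Fasted |
| T-R | 6 | Fed only | Fasted | Fed |

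Under SAP 7.8.2, 6 of 6 values in each column precede the labelled treatment: 6 + 6 = 12 of 12. Under the protocol rule it is 0 of 12. The rows sit side by side with equal counts, so the column totals (6 and 6) do not reveal the exchange.

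**Step 4: time since the first dose.** Protocol 6.2.2 says: "At least 6 days will separate drug administrations in the first and second treatment periods". The minimum interval is 6 × 24 h − 2 h = 144 h − 2 h = 142 h.

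**Step 5: what is not affected.** The post-exam value follows the second dose, so its assignment to Period 2 agrees with the protocol. Visit 2 laboratory values and the PK endpoints are outside this rule.

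**The case against.** The best defence is that Protocol 7.3.4 hands the detail of assignments and time intervals to the SAP and allows further analysis intervals, and that SAP 7.8.2 uses this freedom openly. The only boundary the protocol spells out is before versus after first intake. Protocol 6.2.2 also counts Day -1 to Day 5 as belonging to each period, so a sample two hours before the second dose lies within Period 2, and assignment by period could be called a reasonable reading. This does not remove the conflict. The SAP may detail the intervals, but within the stated principle of actual treatment at the planned time. The day listing in 6.2.2 is a visit schedule, not a rule for attributing data.

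Several narrower points do stand:

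- The protocol sentence "For all analyses, the treatment actually administered (= treatment at onset) to the subject will be used" mainly concerns deviations from the randomised treatment. It is weak support, and the argument does not need it.
- The AE phases do not formally govern laboratory data. Different conventions are not in themselves an error.
- The Flow Chart, the sponsor's laboratory standard and the analysis dataset plan are not available, and there are no table shells. A row visibly marked -2:00 would warn a careful reader, although its change from baseline would still sit under a treatment not yet taken.
- The practical consequence is small. The tables are descriptive, individual values are listed by sequence and visit, and out-of-range values are flagged. A change judged clinically relevant is recorded as an AE and, with onset before the second dose, goes to the Period 1 treatment.

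**Conclusion.** The concern holds, as a minor point. SAP 7.8.2 assigns one laboratory time point against the principle in Protocol 7.3.4 and against the SAP's own reason for rejecting a Period 2 laboratory baseline, and Section 4 does not declare the departure.

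Twelve values are misassigned if all 12 subjects complete with 6 per sequence. The clinical size cannot be estimated, because the documents give no laboratory effect at 142 h or later after a dose, and it may be zero. What is misplaced is mainly the summary of changes not judged clinically relevant.

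The conclusion rests on reading V3 -2:00 as two hours before the second dose. Any other meaning in the Flow Chart would need to be checked against it.

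**What to change.** In SAP 7.8.2, either assign V3 -2:00 and its change from baseline to the Period 1 treatment, or show it as a separately labelled pre-dose row for Period 2 outside the by-treatment summary. Keep post-dose Visit 3 values and the end-of-trial examination under the Period 2 treatment. If the sponsor wants to retain the present rule, it should be listed in SAP Section 4 with a reason.

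The cost is one sentence in the SAP and one visit-to-treatment mapping in the analysis dataset. No new data are needed.
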